groups were found on alcohol consumption. For comparing the longitudinal profile of the substance use outcomes (standard drinks/day, peak standard drinks/day, # drinking days, # binge drinking days) using repeated measures analysis assuming 3 measurement time points, level of significance  $\alpha=0.05$ , two-tailed comparison, correlation between pairs of measurements within participants no larger than  $\rho=0.5$ , we estimate that 50 participants per group (total  $n=100$ ) are needed to achieve a power of 89% to detect a difference of 0.5 standard drinks between GMI and CT. A sample size of 65 ( $n=130$ ) will provide 83% power to detect a difference of 0.4 standard drinks between treatment conditions. The corresponding sample size requirements after adjusting for a 30% dropout rate are 142 (71 per group) and 186 (93 per group), respectively. To account for the “fraction of missing” information that must be imputed in the intent-to-treat (ITT) sample and the dilution effect of ITT analyses, we further inflate the sample size by 30% to achieve a final ITT sample size of 93 participants randomized to GMI and CT (total  $N = 186$ ) to detect a difference of 0.4 standard drinks between treatment conditions. For the global statistical test (GST), when the collection of outcomes (e.g., standard drinks/day, etc.) show consistent directionality with regard to improvement, GST will have higher power than that of tests of single outcomes.

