## **C12. Overview of the statistical analysis plan.**

**Effectiveness analyses:** all health services and participant outcomes (see section C9) will be obtained at three time points (month 1, 3 and 6-months post-randomization). These variables include: (a) Substance use outcomes (e.g., standard drinks/day (SEC), peak standard drinks/day, # drinking days, # binge drinking days, # illicit drug use days, etc.); (b) Treatment engagement (e.g. # of substance abuse/mental health treatment sessions attended, # AA sessions attended, # AA sponsor contacts; (c) Psychosocial adjustment (social support, community participation) and (d) Quality of life/psychiatric indices (QOLS, SF-12, BSI-18); (e) Engagement in structured/productive work activities (% of days each month engaged in work or volunteer activities); (c) Process measures (CPOSS-VA, HAQ) will be assessed at 1-month follow up.

**Analysis sets.** The ITT sample comprises all randomized participants. The per-protocol/completer sample comprises participants who are compliant with protocol requirements and for whom all required measurements have been made. Primary analyses will be carried out using the ITT analysis set.

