sensitivity analysis will be made to balance between model complexity and reduction in bias. We will use Poisson distribution with a log-link for count outcomes (e.g., # drinking/drug use days, # days SUD treatment, # days structured work activities), Binomial distribution with logit-link for binary outcomes (e.g. attended treatment/did not attend treatment) and Gaussian distribution with identity-link for continuous outcomes (e.g., standard drinks). When we suspect over-dispersion in the count models that is beyond what is assumed by the Poisson GLMM then we will use Negative Binomial distribution. To deal with zero inflation, we will use zero-inflated Poisson (ZIP) and negative binomial (ZINB) models. For multiple outcomes, we will use a joint model based on linking the GLMM models for each outcome type by assuming a joint statistical distribution for the random coefficients (intercept and slopes). Let  $Y_{ijk}$  be the response from the  $k$ th outcome for subject  $i$  at occasion or time  $j$  ( $i=1, \dots, n$ ;  $k=1, \dots, K$ ;  $j=1, 2, \dots, n_i$ ). The GLMM can be given as,  $E(Y_{ijk} | X_{ij}(t), Z_{ij}) = g^{-1}(X_{ij}(t)\beta_k + Z_i b_{ik})$ , where  $b_{ik} \sim N(0, G_k)$  and  $X_i$  and  $Z_i$  represent vectors of fixed and random effect covariates, respectively, and  $G_k$  is the covariance matrix for  $b_{ik}$ . We will use a random coefficient model with shared random intercept and random slope for each outcome. The resulting 'over all' covariance matrix (D) from this model will provide standard error estimates that account for correlation among the multiple outcomes. A key assumption for these models is conditional independence where the responses are independent given the random effects. These models can be fitted using Proc NLMIXED or GLIMMIX in SAS v9.3.

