**C12d. Analysis plan for Clinical, Social, and Quality of Life outcomes (Specific AIM I; Hypotheses 1 through 4):** To evaluate the relative efficacy of (a) GMI and (b) CT on (a) five health services outcomes (i) substance use (ii) treatment engagement, (iii) psychosocial integration (e.g., social support, community participation), (iv) quality of life/psychiatric indices, and (v) # of days engaging in structured/productive work activities. The longitudinal trajectory of efficacy outcomes will be compared using the GLMM approach, which accommodates missing at random (MAR) data and a wide range of data types/distributional assumptions: counts (e.g., # AA sessions, # times talking with AA sponsor, # substance abuse treatment sessions attended); dichotomous (e.g., abstinent/not abstinent), proportions (proportion days not drinking alcohol or using illegal drugs), and ordinal (e.g. CPOSS-VA, QOLS). When the number of zeroes is in excess of what is normally expected from a poisson model, we will fit GLMM to accommodate zero-inflation. We will use negative binomial regression to deal with over dispersion. Logit link for dichotomous outcomes, log link for count outcomes will be considered. The basic modeling procedure involves using the longitudinal outcome measurements within each of the domains separately as the dependent (outcome) variable, with intervention group (fixed effect), time (random effect), and time by intervention as the primary independent variables. In further multivariable modeling, additional covariables (as appropriate for a given dependent variable) will be added to the basic model to adjust for potential confounding effect of these variables. GLMM accommodates both fixed and time-varying covariates. For example, for the treatment engagement variable, the # of AA sessions measured monthly for 6 months will be an outcome variable, intervention group (GMI, CT), time, and time X intervention will be the primary independent variables in the basic (unadjusted) model, and psychiatric comorbidity (number and severity), age, race, and gender will be added in the subsequent (adjusted) model to adjust for the possible confounding effect of these variables. Unadjusted and covariate-adjusted least squares means for each outcome variable will be compared at the primary time point (month 1) and at intermediate secondary time points (months 3 and 6) using appropriate model contrasts and the Tukey-Kramer adjustment for multiple comparisons for the secondary time points. These contrast comparisons, along with corresponding 95% CI, will provide estimates of the difference in outcome means (effect sizes) for the hypothesized comparisons. For longitudinal dichotomous outcomes (e.g., maintenance of sobriety), we will compare unadjusted and covariate-adjusted proportions across the longitudinal trajectory (at 1, 3 and 6 months) for GMI and CT. For the end-of-active treatment time point, this analysis is equivalent to a logistic regression analysis.

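### The 83% power in C11 matches an arm difference averaged over months 1, 3 and 6, which C12d does not specify; the month-1 contrast C12d names as primary has about 63%

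*Combined protocol and SAP*

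**What the plan says.** C11 introduces its power calculation with "For comparing the longitudinal profile of the substance use outcomes". It assumes three measurements, alpha 0.05, a "two-tailed comparison" and within-person correlation no larger than 0.5. It says that 50 per group "are needed to achieve a power of 89% to detect a difference of 0.5 standard drinks between GMI and CT", and that 65 per group "will provide 83% power to detect a difference of 0.4 standard drinks between treatment conditions". Allowing for 30% dropout, 65 becomes 93 per arm. No SD is given, and the contrast being powered is not named.

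C12 says that the outcomes "will be obtained at three time points (month 1, 3 and 6-months post-randomization"; baseline is not in that list, although C9 measures it. C12c adds: "We will use a random coefficient model with shared random intercept and random slope for each outcome". C12d says: "The longitudinal trajectory of efficacy outcomes will be compared using the GLMM approach", in a model "with intervention group (fixed effect), time (random effect), and time by intervention as the primary independent variables". C12d then compares least squares means, with month 1 as the primary time point and months 3 and 6 as secondary, and says these contrasts estimate the effect sizes for the hypothesized comparisons. It does not say whether time is numeric or categorical, or whether baseline is a response. It defines no contrast averaged over visits.

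**The concern.** Three different quantities could be taken as the efficacy result: the arm difference averaged over visits, the month-1 arm difference, and the time-by-intervention term. They have different null hypotheses and different power, and C11 gives one figure without saying which quantity it belongs to.

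The distinction matters in this design. C1 puts all four sessions in Week 2, before the first follow-up, so a successful intervention may well show as a shift already present at month 1. If that shift persists, the two arms run parallel, and a test of equal slopes has a true null even though GMI works. If the shift fades, the slope test can reject in the direction against GMI. A reader who took the 83% as the chance of success on either the month-1 contrast or the trajectory term would be misled.

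**Working it through.** **Inputs.** From C11: two-sided alpha 0.05, 65 per arm for 0.4, 50 per arm for 0.5, three measurements, correlation at most 0.5. From C12: months 1, 3 and 6. Assumed: SD 1 (so 0.4 means 0.4 SD), Gaussian outcome, and correlation 0.5 as either AR(1) by visit order or compound symmetry (CS). C12b names both structures.

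**Formula.** For a contrast L with within-person covariance V, SE = sqrt((2/n) × L'VL), z = estimate/SE, and power = Φ(z − 1.96) + Φ(−z − 1.96).

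**1. Reproduce C11 with the average over three visits.**
- AR(1): L'VL = (3 + 2(0.5 + 0.5 + 0.25))/9 = 0.611. At n = 65, SE = sqrt(2 × 0.611/65) = 0.137, z = 0.4/0.137 = 2.92, power 83.1%. At n = 50 with 0.5, SE = 0.156, z = 3.20, power 89.2%. Both stated figures are matched.
- CS: L'VL = (3 + 2 × 1.5)/9 = 0.667. Power is 79.8% at n = 65 and 86.5% at n = 50.

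**2. The month-1 contrast, 65 per arm, true difference 0.4.**
- Month-1 data alone: SE = sqrt(2/65) = 0.175, z = 2.28, power 62.6%.
- Fitted at month 1 from a straight line through months 1, 3 and 6 by generalised least squares (GLS): estimate 0.40 (unbiased), power 65% (AR(1)) or 68% (CS).
- Month 1 adjusted for baseline as a covariate, correlation 0.5: SE = 0.175 × sqrt(0.75) = 0.152, power 75.0%.

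None of these reaches 83%.

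**3. The time-by-intervention term with numeric time, months 1, 3 and 6, 65 per arm.** The GLS slope weights sum to zero: (−0.172, −0.047, 0.219) under AR(1). A sustained 0.4/0.4/0.4 therefore gives a slope difference of 0, and the rejection rate equals alpha, 5%, under either structure. With a fading effect of 0.4/0.2/0, the test rejects 45% (AR(1)) or 62% (CS) of the time, essentially all in the direction against GMI.

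**4. The same term with baseline added as a response (0/0.4/0.4/0.4 at months 0, 1, 3, 6).**
- AR(1): slope 0.0436, SE 0.0370, z = 1.18, power 22%.
- CS: slope 0.0476, SE 0.0271, z = 1.76, power 42%. A random-slope variance on top of CS lowers this, for example to 31.5% at 0.01 and 17.0% at 0.05 per month squared; the documents give no value.
- The fitted month-1 contrast is pulled towards the baseline zero. Its estimate is 0.19 (AR(1)) or 0.23 (CS) instead of 0.40, with power 29% or 35%.

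**The case against.** A reader might infer something stronger: that the plan as a whole would detect a sustained effect only 5% of the time, against a claimed 83%. The documents do not support that. C12d lists intervention, time and their interaction as model terms; it never names the interaction as the test of H1-H4. It goes on to specify least squares mean contrasts at months 1, 3 and 6 and ties those to the hypothesized comparisons. They test differences in outcome. With post-baseline responses only, the month-1 contrast is unbiased for a sustained effect even when time is linear.

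It is also fair to say that linear time is not stated. C12c keeps fixed and random covariates separate, so a random slope does not force a straight line in the fixed effects. Nor is it certain that the effect is complete by month 1: both arms are offered a booster two months after the intervention (C7), and a slope term would be informative for an effect that grew.

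All of this limits the trajectory point to one term under one reading. It does not answer the main point. The power in C11 matches a contrast that C12d does not contain, and the contrast C12d does name is less well powered. C12d also does not rank the trajectory comparison against the contrasts, and the wording on time as a random effect with random slopes does point towards numeric time.

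**Conclusion.** The concern holds as a mismatch between the powered quantity and the specified contrasts. C11's two figures fit the visit-averaged difference (83.1% and 89.2% under AR(1); 79.8% at 65 per arm under CS). The named primary month-1 contrast has about 63% at 65 per arm from month-1 data alone, or 65-68% from a linear post-baseline fit.

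The trajectory term should not be read as an efficacy test. If time is numeric, its power for an effect complete by month 1 and sustained is 5%, or 22-42% with baseline as a response. If baseline is a response on the same line, the month-1 contrast itself is biased to 0.19-0.23. The documents settle neither condition.

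All figures assume SD 1, Gaussian outcomes, correlation 0.5 and 65 completers per arm. They ignore clustering by workshop or recruitment week and multiplicity across outcomes. Many of the H1 outcomes are counts, for which these figures are only a guide.

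**What to change.** In C12d:
- Enter visit (months 1, 3, 6) as a categorical fixed effect with visit-by-arm terms, and state that baseline is not fitted on the same straight line as follow-up.
- Choose one of two options. Either make the GMI-CT difference averaged over months 1, 3 and 6 the efficacy contrast, and say in C11 that the stated power refers to it, with the SD and correlation structure assumed. Or keep month 1 as primary and restate its power, about 63% at 65 per arm if SD is 1.
- State that H1-H4 rest on the arm contrasts, and that time-by-intervention only describes whether an effect grows or fades.

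The cost is SAP wording and model code. Categorical visit uses a few degrees of freedom, and keeping month 1 as primary means a less favourable stated power. No new data or participants are needed.

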## C9. Outcomes and Assessments

Measures used in this study include those for establishing eligibility and baseline descriptive information (e.g. demographics). *To reduce follow-up losses, participants will be asked to list the names/contact information of 2 family members (or close contacts).* We listed specific assessments in clusters associated with their specific aims and primary/ secondary hypotheses (H1 to H4) for ease of reference. Assessments will be administered at baseline, 1, 3 –and 6-month follow-up visits. A project coordinator trained in the administration of assessment interviews will conduct baseline assessments and a *full-time* research assistant blind to study condition (independent assessor) will administer follow-up assessments (see budget justification for more detailed role designations). After informed consent procedures, participants will complete a battery of assessments taking ~ 94 minutes at baseline and ~70 minutes at follow-ups.

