**C12c. Multiple outcome variables.** We acknowledge concern about inflation of Type I error. This concern must be balanced with the need to avoid overly conservative Type I (false positive) error rates that may result in excessively high Type II (false negative) error rates. As a standard method of balancing these concerns, we will use multivariate GLMM to jointly model the correlated outcomes and study the relationship between the multiple outcomes and treatment. For each outcome ( $Y_{ij}$ ), we consider the model,  $E(Y_{ijk} | X_{ij}(t), Z_{ij}) = g^{-1}(X_{ij}(t)\beta_k + Z_{ij}b_{ik})$ , where  $g$  is a monotone link function,  $b_{ik} \sim N(0, G_k)$  and  $Y_{ij}$  is the response for the  $i$ th subject at the  $j$ th time with  $n_i$  ( $n_i-1, \dots, 10$ ) repeated measurements,  $X_{ij}$  and  $Z_{ij}$  represent vectors of fixed and random effect covariates, respectively, and  $G$  is the covariance matrix for  $b_i$ . If  $b_i$  is a vector of random intercept and slope, it indicates that there is natural heterogeneity among individuals in both their baseline level and changes in the expected outcomes over time. In addition to the variability in the random effects, a diagonal R-side covariance matrix of the form  $2\ln$  is included to account for random error. When the random error is suspected to have more measurement error than what is typically expected then we will use AR(1) R-side covariance matrix. Additional

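### The Aim I outcomes are measured at baseline, but the stated model does not use that value, and neither the unadjusted nor the adjusted month-1 comparison is named as the primary result

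*Combined protocol and SAP*

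**What the plan says.** **Baseline is collected.** Section C9 states "Assessments will be administered at baseline" and at the 1-, 3- and 6-month visits. Table 4 gives this schedule for nearly every instrument under H1 to H4; one test listed under H3 is given at baseline and month 3 only.

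**The analysis plan does not place it.** C12 says the outcomes "will be obtained at three time points (month 1, 3 and 6-months post-randomization". C12d describes the basic model as one "with intervention group (fixed effect), time (random effect), and time by intervention as the primary independent variables". For the adjusted model, "additional covariables (as appropriate for a given dependent variable) will be added to the basic model". The only example concerns AA sessions: psychiatric comorbidity, "age, race, and gender will be added in the subsequent (adjusted) model". The baseline number of AA sessions is not among these covariates.

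**Baseline level is mentioned once in the model text.** C12c says that a random intercept and slope would indicate "natural heterogeneity among individuals in both their baseline level and changes in the expected outcomes over time". This explains what random effects represent. It does not say how the measured baseline value enters the model.

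**Two month-1 results, unranked.** C12d: "Unadjusted and covariate-adjusted least squares means for each outcome variable will be compared at the primary time point (month 1"), and at months 3 and 6 as secondary time points. The word primary is attached to the time point, to the model terms and, in C12, to the ITT set. It is not attached to either of the two results.

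**Housing covariates.** C4 records housing programme and time in VA housing, and makes them covariates if differences are found. It does not say differences in what, or by what criterion.

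**The concern.** There are two linked gaps. First, the baseline value of an outcome is often among its better predictors, and adjusting for it narrows the confidence interval of the arm comparison. A model with only arm, time and their interaction on post-randomisation visits makes no use of it. The open covariate clause allows baseline adjustment but does not commit to it.

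Second, each outcome will have two month-1 estimates. If one is significant and the other is not, nothing in the plan says which is the primary result. The adjusted model is also not fixed, because its covariates are chosen outcome by outcome and the two housing covariates depend on what the data show.

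At stake are avoidable loss of power and an unclear primary result. Validity under randomisation is not at stake.

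**Working it through.** **Inputs.** From C11: two-sided alpha 0.05; three measurement times; within-participant correlation at most 0.5; 65 per arm for a difference of 0.4 with 83% power; 50 per arm for 0.5 with 89% power; 93 per arm after a 30% dropout allowance. C11 gives no SD, so I assume SD = 1 and read 0.4 as 0.4 SD. The correlation r between baseline and month 1 is not given, so I show 0.1 to 0.5. Low values are plausible because C4 requires substance use in the 30 days before consent, which may restrict the spread at baseline. I assume a Gaussian outcome, complete data and no clustering.

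**Formula.** Power = Φ(d / √(2v/n) − 1.96), where v is the variance of the summary being compared.

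**Step 1: C11's own figures (mean of three visits).**
- Equal correlation 0.5: v = (1 + 2 × 0.5)/3 = 0.667. Power is 79.8% (n = 65) and 86.5% (n = 50), short of the stated 83% and 89%.
- AR(1) at 0.5, equally spaced visits: v = (3 + 2 × (0.5 + 0.5 + 0.25))/9 = 0.611. Power is 83.1% and 89.2%, which matches.
- Equal correlation 0.42, which the stated upper bound allows: v = (1 + 2 × 0.42)/3 = 0.613. Power is 82.9% and 89.1%, which also matches.

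Two different structures fit, so C11 does not identify the correlation pattern. I do not call its figures wrong.

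**Step 2: month 1, 65 per arm, d = 0.4.** Without baseline, v = 1. With baseline as covariate, v = 1 − r². The equivalent n is 65/(1 − r²).

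| r | v | Power | Equivalent n per arm |
|---|---|---|---|
| baseline not used | 1.00 | 62.6% | 65 |
| 0.1 | 0.99 | 63.0% | 66 |
| 0.2 | 0.96 | 64.3% | 68 |
| 0.3 | 0.91 | 66.7% | 71 |
| 0.4 | 0.84 | 70.1% | 77 |
| 0.5 | 0.75 | 75.0% | 87 |

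**Step 3: month 1 with nobody lost (93 per arm).** Without baseline, power is 77.9%. With it, power is 81.6% at r = 0.3 and 88.3% at r = 0.5.

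**Step 4: mean of the three visits, 65 per arm.** The adjusted variance is v minus the squared covariance with baseline.
- AR(1) at 0.5, baseline as the preceding equally spaced visit: covariance (0.5 + 0.25 + 0.125)/3 = 0.2917; 0.6111 − 0.0851 = 0.526. Power goes from 83.1% to 88.2%.
- Equal correlation 0.42: 0.6133 − 0.1764 = 0.4369. Power goes from 82.9% to 93.2%.

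The longitudinal gain is therefore about 5 to 10 points, depending on a correlation structure that the plan does not fix.

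**The case against.** **The gain may be negligible.** At r = 0.1 to 0.2 it is 0.4 to 1.8 points, and the entry criterion makes low r plausible. This stands; the case for a useful gain needs r of about 0.3 or more.

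**62.6% is not the plan's model.** C12c describes random intercepts and slopes, so a month-1 estimate may borrow from later visits. With linear time at months 1, 3 and 6 and correlation 0.5 throughout, v = 0.5 + 0.5 × (1/3 + 5.444/12.667) = 0.882, and power is 68.0%. The starting level does move. Baseline adjustment still helps on the same assumptions: v falls by 0.25 to 0.632, and power is 81.8%.

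**Many H1 outcomes are counts.** Drinking days, binge days, sessions and AA contacts would use Poisson, negative binomial or zero-inflated models. This stands: the figures apply to Gaussian outcomes only.

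**Baseline may already be in the model.** The remark on baseline level in C12c, and the talk of trajectories, allow baseline to be read as a repeated response. That does not settle the matter: an unconstrained arm contrast at month 1 would still not be baseline-adjusted.

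**Readings that go too far.** A reader might infer that leaving baseline out biases the comparison; in a randomised comparison it does not. A reader might infer that the team could report whichever result is favourable; C12d commits to both, so the gap is the missing ranking. A reader might infer that the time-by-arm change from baseline to month 1 is the primary test, with much lower power at low r; C12d names month-1 least squares means as the comparison, and the interaction only as a model term.

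**Conclusion.** The point holds as a recommendation that should be acted on. The documents do not state the role of the baseline outcome, and they do not say whether the unadjusted or the adjusted month-1 contrast is the primary result for an outcome.

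For a Gaussian outcome at 65 per arm, the month-1 gain from baseline adjustment is negligible at r = 0.1 to 0.2 and about 4 to 12 points of power at r = 0.3 to 0.5. At 93 per arm it is about 4 points at r = 0.3 and 10 at r = 0.5. These sizes rest on an assumed SD of 1, an assumed r, complete data and no allowance for randomisation by recruitment week. I claim no size for the count outcomes or for the housing covariates.

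Naming one contrast per outcome does not say how the many H1 outcomes combine into a single conclusion. That is a separate question.

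**What to change.** In C12d:

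1. For each outcome whose baseline measurement varies between participants, include the baseline value in the primary model. Enter it either as a covariate (and then not also as a response) or as a response with arm means constrained equal at baseline. Both recover the precision. Exempt any outcome that the entry criterion makes constant at baseline, such as abstinence from all substances over the 30 days before consent.
2. For count and zero-inflated outcomes, fix in advance the transformation of baseline and which part of a two-part model takes it.
3. State that the month-1 contrast from this model is the primary result for that outcome. Report the unadjusted contrast as a sensitivity analysis.
4. Keep the outcome's own measurement times (for AA sessions, "the # of AA sessions measured monthly for 6 months will be an outcome variable") and whatever random effects for recruitment week or group the plan otherwise uses.
5. For treatment encounters counted from the medical record, state the baseline look-back window if a baseline value is to be used; C9a gives none.

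In C4, replace the conditional rule with a choice made before outcome data are seen: always include housing programme and time in housing, or label that adjustment exploratory.

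The cost is wording. Table 4 already schedules the baseline instruments and C4 already records the housing variables; only the record-based counts may need a defined window.

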### **C11. Sample Size Calculation and Power Analyses.**

For sample size calculations, preliminary data from [name] and colleagues were used. In [name] and colleagues, participants in GMI attended a significantly higher number of outpatient SUD treatment sessions compared to their counterparts in TAU. Using zero inflated negative binomial regression (ZINB) and accounting for group level nesting, at 3-month follow-up, participants in GMI attended significantly more outpatient mental health treatment sessions compared to TAU,  $b = .944 (.307)$ ,  $t = 3.079$ ,  $p < .001$ ; Cohen's  $d = .54$ . The efficacy of GMI relative to TAU for lowering substance was assessed among the same sample of dually diagnosed Veterans using ZINB. At 3-month follow-up, participants in GMI consumed significantly less alcohol in standard drinks ( $b = -155.3 (70.9)$ ,  $t = -2.19$ ,  $p = .03$ ; Cohen's  $d = .36$ ) and drank fewer standard drinks in terms of peak (highest) alcohol drinking day ( $b = -4.78 (2.03)$ ,  $t = -2.4$ ,  $p = .02$ ). No baseline differences between

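### C12d names month 1 as the primary time point, but C11's 83% power is for a three-visit profile; separately, no rule says what makes H1 positive

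*Combined protocol and SAP*

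**What the plan says.** **Time point.** In C12d, unadjusted and covariate-adjusted means for each outcome "will be compared at the primary time point (month 1) and at intermediate secondary time points (months 3 and 6"). The same section says that the longitudinal trajectory will be compared by GLMM. It does not say which of the two decides. The basic model is specified "with intervention group (fixed effect), time (random effect), and time by intervention as the primary independent variables". In the worked example, "psychiatric comorbidity (number and severity), age, race, and gender will be added in the subsequent (adjusted) model". The baseline value of the outcome is in neither list.

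**Power.** C11 compares the longitudinal profile of the substance use outcomes "using repeated measures analysis assuming 3 measurement time points", at two-sided 0.05, with "correlation between pairs of measurements within participants no larger than" 0.5. It gives 89% power for 0.5 standard drinks with 50 per group. A sample of 65 per group "will provide 83% power to detect a difference of 0.4 standard drinks between treatment conditions". Allowing for 30% dropout gives 93 per group. No SD or formula is stated. The supporting evidence cited in C11 is at three months: "At 3-month follow-up, participants in GMI consumed significantly less alcohol in standard drinks".

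**H1 outcomes.** C12 lists five substance use measures and leaves the list open. It then lists "Treatment engagement (e.g. # of substance abuse/mental health treatment sessions attended, # AA sessions attended, # AA sponsor contacts". The Data Monitoring and Safety Plan adds drinks per drinking day.

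**Multiplicity.** C12c acknowledges Type I inflation and offers a joint GLMM whose standard errors allow for correlated outcomes. Tukey-Kramer in C12d covers the secondary time points. The global statistical test (GST) appears in C11 as a remark on power and is not taken up in C12.

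**The concern.** The sample size justification and the comparison labelled primary concern different quantities. A single visit usually carries less information than an average of three, so 83% cannot simply be carried over to month 1. If month 1 decides, the trial may run with materially less power than its readers believe. If the trajectory decides, the month-1 label is misleading.

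The second gap is about inference. H1 covers two domains and at least eight outcomes, and the plan does not say whether one, some or all must succeed. The dissemination plan in C13 is conditional on positive findings, so what counts as positive needs to be settled before the data are seen.

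**Working it through.** **1. Inputs.** From C11: two-sided alpha 0.05, three visits, correlation at most 0.5, 0.4 drinks with 65 per arm (83%), 0.5 drinks with 50 per arm (89%), 30% loss. From C3: 93 per arm randomised and a 13% drop-out rate in the earlier trial. Evaluable per arm: 93 × 0.70 ≈ 65; 93 × 0.87 ≈ 81; no loss, 93. Assumed, because C11 does not give them: the SD, the correlation structure, equal variance at each visit, and the same 0.4 effect at month 1 as on average.

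**2. Reproducing C11.** Take the difference in three-visit means. With variance V per participant, power ≈ Φ(Δ/√(2V/n) − 1.96).

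- AR(1) 0.5, SD 1: V = [3 + 2(0.5 + 0.5 + 0.25)]/9 = 0.611. For 0.4 and n = 65: 0.4/√(2 × 0.611/65) = 2.917, and Φ(0.957) = 83.1%. For 0.5 and n = 50: 89.2%.
- Compound symmetry 0.5, SD 0.96: V = 0.667 × 0.96² = 0.614, giving 82.9% and 89.1%.
- Compound symmetry 0.5, SD 1: 79.8% and 86.5%, which does not match.

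So a three-visit average reproduces both stated figures under two readings. This is inferred from the fit; C11 does not say it.

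**3. Month 1 under the same readings.** Unadjusted with SD 1, V = 1: 0.4/√(2/65) = 2.280, and Φ(0.320) = 62.6% (noncentral t, 61.9%). The table uses the noncentral t and Δ = 0.4.

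| Month-1 contrast | 65 per arm | 81 per arm | 93 per arm |
|---|---|---|---|
| Unadjusted, SD 1 to 0.96 | 62–66% | 72–75% | 77–81% |
| Time modelled as linear (V = 0.9375 for AR(1), SD 1; 0.882 × 0.96² for compound symmetry) | 65–71% | 74–80% | 80–85% |
| Baseline-adjusted, correlation 0.5, SD 1 (V = 1 − 0.5² = 0.75) | 74% | 83% | 88% |

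For an unadjusted month-1 contrast to match what C11 gives to 65 per arm, the number evaluable would be 65/0.667 = 98 (compound symmetry) to 65/0.611 = 107 (AR(1)) per arm.

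**4. How far the assumptions move this.**

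- SD, unadjusted, at 65 and 93 per arm: 81% and 92% if SD is 0.8; 44% and 58% if SD is 1.25.
- Variance pattern: with equal variances, month 1 has 1.50 to 1.64 times the variance of the three-visit mean at correlation 0.5. With illustrative SDs of 1, 1.2 and 1.4 at the three visits the ratio is 1.04 to 1.13; with 1, 1.2 and 1.5 it is 0.98 to 1.07.
- Effect over time: if the month-1 effect were 0.5 (SD 1, unadjusted), power is 81% at 65 and 92% at 93.
- Baseline correlation 0.7 (SD 1): 89% at 65 by the normal approximation.
- Clustering by group: at an assumed ICC of 0.05 and 3 to 6 per group, the design effect is 1 + (m − 1) × 0.05, and the unadjusted SD 1 figure at 65 falls to about 53–58%.

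**5. H1.** C12 names 5 + 3 = 8 outcomes, and the monitoring plan makes nine. Correlation-aware standard errors do not by themselves limit false positives over separate contrasts. Tukey-Kramer does not reach the month-1 contrasts, and the GST has no role in C12. As an illustration only, suppose any one of eight tests at 0.05 sufficed. Under independence the family-wise error is 1 − 0.95⁸ = 34%. By simulation it is 24% with correlation 0.7 within and 0.2 across domains, and 19% with 0.7 throughout.

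**The case against.** The strongest reply is that C12d also compares the trajectory, and the Data Monitoring and Safety Plan repeats this without naming a primary time point. On that reading C11 powers the intended analysis and month 1 is one contrast within it. This stands to the extent that the text is unresolved. A reader might infer that month 1 is the sole primary analysis, but the documents do not go that far. They attach the word primary to month 1 and leave the ranking open.

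A reader might also infer that the month-1 contrast is certainly underpowered, or that one visit has at least 1.5 times the variance of the average whatever the SD. Neither is supported. The 1.5 factor needs equal variances, and many H1 outcomes are counts whose variance moves with the mean. The covariate list in C12d is an open example, so baseline adjustment is unspecified, not excluded. The 65-per-arm case spends the whole 30% loss allowance by the first follow-up. C2a reports one-month differences in binge drinking and drug use days, so an early effect is plausible.

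On multiplicity, the plan does address the issue through the joint model, and it nowhere adopts an any-one-of-eight rule. What remains is that no power is stated for the contrast called primary, and no rule turns the H1 results into a conclusion.

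**Conclusion.** Both gaps are real and should be closed; the size of the first is conditional.

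- **Power.** C11's 83% does not describe the month-1 contrast. Under SDs and correlations that reproduce C11, with equal variances and a constant 0.4 effect, unadjusted month-1 power is about 62–66% at C11's own 65 per arm. It stays below 83% even with all 93 observed. Linear time or baseline adjustment narrows the gap, and with low month-1 loss, a smaller SD, a larger early effect or a strong baseline correlation month 1 could reach 83% or more. Clustering works the other way. Because C11 gives no SD, the true figure cannot be fixed from the documents.
- **H1.** No stated procedure controls Type I error over the H1 contrasts or defines a positive result. The 19–34% range shows what one possible reading would cost and is not the plan's error rate. C11's power calculation also covers substance use only, so the engagement half of H1 has no stated power.

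**What to change.** **Reconcile C11 and C12d, and rank the trajectory comparison.** Either:

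1. make the arm difference averaged over months 1, 3 and 6 the primary contrast, with single months secondary; or
2. keep month 1 and restate its power with the SD, expected month-1 loss, baseline-outcome adjustment and clustering.

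In both cases adjust for the baseline outcome, which Table 4 already collects.

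**Give H1 a rule.** Prespecify one test for substance use and one for treatment engagement, with Holm over the two and other outcomes supportive. Each test can be one named outcome, or the GST already cited in C11 if the outcomes are expected to move together. Other error-controlled schemes would also serve. State in C12c that the joint GLMM supplies standard errors and this rule supplies the error control.

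**Cost.** This is SAP wording only, with no new data or participants, but power is paid. At the first Holm step (0.025), SD 1 and before clustering, a single outcome averaged over three visits has about 70–74% power unadjusted at 65 per arm and 80–84% at 81. With baseline adjustment (correlation 0.5) these become 81–90% and 89–95%. The GST on five outcomes correlated 0.7 has 82–86% power at 65 if all respond equally, but 37–40% if only three do. Averaging over visits changes the estimand, and a supportive outcome could no longer establish H1 alone.
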